To manage the pain and discomfort associated with the ureteral stent, some physicians will prescribe pain medications, such as Tylenol, Motrin, NSAIDs, or Opioids. Patients will fall back to any of these pain management medications, specifically Opioids, when their pain is intolerable. Opioid addiction is an epidemic in US, there are numerous initiatives to curb this crisis starting from limiting the number of opioid prescriptions.

In an effort to find new and alternative ways of treating this pain, we are conducting a study on Transcutaneous Electrical Nerve Stimulation (TENS) to measure its effect on reducing the pain caused by ureteral stents and compare it to the standard of care practice that does include various pain management medications.

In this study, the team is proposing to recruit 60 patients who underwent a kidney stone procedure with a post procedural ureteral stent. Thirty of the sixty patients will be randomized

and discharged with a TENS device (treatment group) that they will use over a course of 3-7 days (typical duration of a stent in the patient) to see how the device helps in treating their pain associated with the stent. The electrode pad will be applied to the lower back near the paravertebral position and the site of pain (Figure 3). The remaining 30 randomized patients will be in the control group, and will not receive a TENS device. All 60 patients are required to complete a daily pain visual analog score (VAS) score along with their daily pain medication intake. Once the stent is removed in the physician's clinic during their follow up visit, they will hand over the TENS and complete a survey of their experience and pain score with the device. These survey results from the treatment group will be compared against the control group to measure efficacy and safety of the TENS device for treating renal colic pain.

The study will not otherwise affect the care a patient will receive. The TENS group will receive the same standard of care treatment as the non-TENS group, but the TENS group are asked to use the TENS device 4 times a day for 60 minutes during each treatment while they have the ureteral stent placed in their body.

Objectives:

- 1) Primary outcome – To determine the patient with the TENS unit had a lower reported pain and nausea VAS score compared to control (non-TENS) group

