- 2) Secondary outcome – To determine the patient with the TENS unit took less number of opioids during the duration of stent placed in their ureter compared to control (non-TENS) group

Methods and Measures

This will be a randomized control trial with subjects randomized to either the standard of care pain-relief group or an FDA-cleared TENS unit. The TENS group will follow the standard of care pain-relief group if they are intolerance to TENS or they are seeing no benefits from the TENS unit during the duration of the study. If they stop using TENS or continue following the standard of care treatment intervention, they will document such in the daily survey form.

Participants will be enrolled when they are seen in the Urology clinic for their ureteroscopy procedure scheduling. Participants with kidney stones who are consented for a ureteroscopy will be eligible for the study. Participants will be informed during the enrollment and consent process that if they decide to participate in the study, they will be randomized to receive a TENS unit or the typical standard of care treatment. They can elect to decline the enrollment based on that information, or if they choose to enroll, then they will sign the consent form for participating in the study.

Randomization participants using random generator will be performed by the urology physicians or residents in the preop area of the [name] hospital. The patient will be notified in the preop are which study group they are being assigned to, and they will be given further instructions and training post-ureteroscopy procedure in the PACU area. TENS group will be discharged with a TENS unit along with training and instructions on how to use the device. All participants will be instructed to complete a daily survey at the end of day and a final

survey at the time of stent removal. All follow up care will be performed remotely. Participants enrolled in the TENS group will return their TENS unit during the stent removal in the physician's office.

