The device settings will be adjusted beforehand and will be the same for every participant, unless it is felt to be too strong, in which case a lower intensity (current intensity with no changes to other stimulation parameters) setting will be used. It should cause no more than minimal tingling to the area on the back where it is applied. The placement of electrode pads will be determined in the PACU area post-ureteroscopy, and the participants will be trained to the device settings and electrode pad placement.

Participant Selection Criteria:

Inclusion

- Adult patients undergoing standard of care ureteroscopy and laser lithotripsy for urinary stone disease
- Patients receiving a stent following their ureteroscopy and laser lithotripsy

Exclusion

- Children
- Pregnant patients
- Patients unable to answer pain questionnaire
- Patients undergoing PCNL
- Patients being treated for Urologic malignancy with ureteroscopy
- Patients who require long term or chronic ureteral stent management
- Patient with implantable stimulators
- Patient with epilepsy
- Patients undergoing laser lithotripsy without stent placement

Sample Size

60 participants with 30 participants in each group

Outcome Measures:

Primary outcome will be to measure and compare daily pain score on a VAS 11-point scale in the TENS group vs control group. Secondary outcome will be the amount of pain medication used in TENS group vs the control group.

Statistical Plan:

The two groups will be analyzed using t-tests or ANOVA, and the final results will be analyzed using descriptive analytics. A regression analysis will be performed for independent outcome prediction.

Recruitment Methods and Consent

All participants will be recruited during their outpatient consultation for kidney stones with the urology clinic. Participants who are scheduled for a standard ureteroscopy procedure with laser

are eligible for the study and they will be informed about the study. The consent form will be shared by the attending physician to the participant during their initial consultation visit and the participants will have sufficient time to make a decision if they want to participate or not. Signed informed consent form will be obtained for each participant before their ureteroscopy procedure.

Reporting of Adverse Events or Deviations

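### Prior opioid use is neither recorded nor adjusted for, which may cost precision in the secondary opioid comparison

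*Combined protocol and SAP*

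**What the plan says.** All references are to the combined protocol and SAP.

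- **Outcome.** The second objective asks whether TENS patients "took less number of opioids during the duration of stent placed in their ureter", compared with control. Outcome Measures describes it differently: "Secondary outcome will be the amount of pain medication used in TENS group vs the control group". Neither gives a unit or says whether a patient's usual medication counts.
- **Eligibility.** Under Participant Selection Criteria the main inclusion criterion is "Adult patients undergoing standard of care ureteroscopy and laser lithotripsy for urinary stone disease". The nine exclusions, among them "Patients unable to answer pain questionnaire", include none on current opioid use or chronic pain. The one item about chronic management concerns stents.
- **Data.** The Background states "All 60 patients are required to complete a daily pain visual analog score (VAS) score along with their daily pain medication intake". This is a diary kept while the stent is in. No record of opioid use before the procedure is described.
- **Analysis.** The Statistical Plan says "The two groups will be analyzed using t-tests or ANOVA, and the final results will be analyzed using descriptive analytics". It adds one regression, meant to predict outcomes, without naming its dependent variable, treatment term or covariates.
- **Allocation and size.** Methods and Measures describes a random generator with no stratification. Sample Size gives only "60 participants with 30 participants in each group".

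**The concern.** A patient who takes opioids every day will probably go on taking them while the stent is in, whatever TENS does. If those doses enter the count, they add differences between patients that have nothing to do with treatment. The window is short, typically 3 to 7 days, so usual doses could be large beside those taken for stent pain, and with 30 patients per arm a few such patients can matter. A t-test leaves this variance in the error term. A regression that includes prior use takes much of it out, but only if prior use was recorded.

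At stake is the chance of detecting a real opioid-sparing effect. The outcome is secondary, but the Background gives reducing reliance on opioids as part of the reason for the trial.

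**Working it through.** **The plan's own figure.** The plan gives no alpha, power, effect size or SD, so 60 patients cannot be reproduced. For reference, at two-sided 5% and 80% power, 30 per arm detects a standardised difference of (1.960 + 0.842) × √(2/30) = 0.72.

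**Assumed inputs, none from the documents.** SD among non-users 4 pills over the stent period; true difference 3 pills (3/4 = 0.75 SD); a share p of patients are prior users, each taking B extra pills; two-sided 5%. Only the 30 per arm comes from the plan.

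**Effect on power.** The variance becomes 16 + p(1 − p)B². The noncentrality of the t-test (58 degrees of freedom) is 3 / (SD × √(2/30)), with √(2/30) = 0.258.

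| p | B | Variance | SD | Noncentrality | Power |
|---|---|---|---|---|---|
| 0 | – | 16 | 4.00 | 2.90 | 81% |
| 5% | 10 | 16 + 0.0475 × 100 = 20.75 | 4.56 | 2.55 | 71% |
| 10% | 10 | 16 + 0.09 × 100 = 25.0 | 5.00 | 2.32 | 63% |
| 5% | 16 | 16 + 0.0475 × 256 = 28.16 | 5.31 | 2.19 | 58% |
| 10% | 16 | 16 + 0.09 × 256 = 39.04 | 6.25 | 1.86 | 45% |

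Milder cases cost less: six prior users with 5 extra pills give 76%, and one with 10 extra gives 78%.

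**Chance imbalance.** Six prior users among 60 split 5:1 or worse with probability 0.19 (hypergeometric). With B = 16, a 5:1 split moves the mean difference by (5 − 1)/30 × 16 = 2.1 pills.

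**What adjustment recovers.** In simulation with six prior users and B = 16, a yes/no covariate raises power from 44% to 81% if every prior user takes the same extra amount. If extra use varies between users (gamma, mean 16), adjusted power is about 69% when its SD is 8 and about 52% when it is 16. If the extra amount were known exactly, the residual SD would return to 4 and power to about 81%; that is the ceiling.

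**Skewed data, second set of assumptions.** Non-user use with mean 5 and SD 5, a true 60% reduction in stent-related use, extra use varying by up to 30% around its mean; 3,000 simulated trials per case. Power with no prior users is 91–92%. Each cell below shows power by t-test, then with a yes/no covariate.

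| Mean extra pills | 3 prior users | 6 prior users | 9 prior users |
|---|---|---|---|
| 10 | 78% → 91% | 67% → 90% | 58% → 91% |
| 20 | 50% → 89% | 34% → 87% | 29% → 87% |
| 40 | 22% → 87% | 14% → 79% | 13% → 72% |

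With no true effect, the t-test rejected in 4.3–5.2% of trials that included prior users.

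**The case against.** The strongest reply is that the t-test remains valid. Its standard error already contains the variance from prior users, randomisation balances them in expectation, and type I error does not rise. This stands. A reader might infer from the 2.1-pill shift that prior users bias the comparison or raise the risk of a false opioid-sparing claim; the documents and the calculations do not support that. A 5:1 or worse split is also the minority case, since about 80% of trials with six prior users would split 4:2 or better.

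Second, the size depends on assumed inputs. This also stands. It is tempting to say that a few prior users would dominate the outcome. That needs heavy usual use, and the documents give neither the share of prior users nor how much they take. The plan makes no power claim for this outcome either.

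Third, the Statistical Plan includes a regression, which could carry prior use. It would therefore be wrong to call the whole plan unadjusted. But the regression names no covariates, and a variable that was not collected cannot enter it.

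Fourth, the outcome itself is not settled. The objective counts opioids and Outcome Measures refers to pain medication in general. That usual doses count at all is an inference from the diary, which asks for daily intake without saying what is included. This stands, and it sets the order of the fix.

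**Conclusion.** The concern holds as a loss of precision on a secondary outcome. Patients already on opioids can enrol, their prior use is not recorded under the plan, and no prespecified analysis takes it into account. Under the first set of assumptions, power falls from 81% to 71% in the mild case and to 45% in the heavier one. If there are no prior users, or if the outcome is defined to leave out usual medication, the loss disappears. There is no systematic bias.

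A reader might extend the point to the pain analysis. Nothing in the documents or in the calculations supports adding the covariate there, so the point is confined to the opioid outcome. Because the remedy is so cheap, it is worth adopting even though the true size is unknown.

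**What to change.** Keep eligibility as it is.

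1. Reconcile the opioid count in the Objectives with the amount of pain medication in Outcome Measures. State one definition, its unit, and whether usual medication is counted.
2. Before allocation, record preoperative opioid use from the medication list: yes/no and usual daily amount.
3. Make the main opioid analysis a prespecified regression on treatment and prior use, stating in advance the form in which prior use enters.
4. Report the result in patients without prior use as a sensitivity analysis.

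The cost is one or two abstracted fields and one model term. If only yes/no is recorded and usual use varies widely, power is only partly recovered, which is the reason to record the amount as well.
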